1.0 PROTOCOL SUMMARY AND/OR SCHEMA

This is prospective double-arm, randomized cross-over clinical trial that will assess whether the addition of a local analgesic agent, ropivacaine, to the standard of care of propofol will reduce the percentage of pediatric neuroblastoma patients who require opioid analgesia after bone marrow procedures compared to propofol alone. A “bone marrow procedure” will be defined as 4 bone marrow aspirations *and* 2-4 bone marrow biopsies. Pediatric neuroblastoma patients will receive the standard of care (Intervention A) or the standard of care with the addition of subcutaneous and periosteal infiltration of ropivacaine (Intervention B). We will compare the percentage of patients requiring post-procedural opioid analgesia in each Intervention as the primary endpoint, as well as total opioid consumption, time to first opioid, percentage requiring non-opioid analgesia, standardized pain scores and quality of life metrics. Based on statistical considerations and extrapolation from an informal needs assessment, we expect to enroll enough patients for adequate power within 6 months of study opening.

2.1 OBJECTIVES AND SCIENTIFIC AIMS

Primary Objective:

- Determine whether there is a reduction in the percentage of pediatric neuroblastoma patients undergoing a bone marrow procedure who require post-procedural opioid analgesia within 24 hours (+/- 4 hours) of the procedure with the addition of local ropivacaine.

Secondary Objective:

Determine whether there is a difference in:

- 24 hours (+/- 4 hours) post-procedure opioid consumption in morphine equivalents (mg/kg/day)
- Percentage of patients requiring non-opioid analgesia within 24 hours (+/- 4 hours) of procedure
- Standardized pain scores (Wong-Baker FACES® Scale)
- Time to first opioid medication
- Short-term quality of life
- Adverse outcomes with the addition of local ropivacaine

3.0 BACKGROUND AND RATIONALE

3.1 **Background**

Pediatric neuroblastoma patients undergo bone marrow aspiration (BMA) and biopsy (BMB) procedures as a part of their extent of disease evaluation at regular intervals during treatment and surveillance. Many studies of both pediatric and adult oncology patients have shown that bone marrow aspirations and biopsies are painful procedures.¹⁻³ Not only do patients report procedural pain, but health care professionals and parents also acknowledge that these procedures are painful. A study asked Italian Pediatric Hematology-Oncology health professionals (medical directors, physicians, nurses, psychologists) their perceptions of procedural pain and found that providers considered BMA and BMB to be above 5 on a scale of 0-10 in 97.5% and 99.5% of cases, respectively.⁴ Another study looking at pediatric oncology patients and their parents showed procedures to be the most frequent cause of distress.⁵ Exposure to repeated painful procedures has been found to exacerbate anxiety and distress in children.^{6,7}

The American Academy of Pediatrics (AAP) developed a report in 1990 stating that strategies to reduce pain and anxiety are integral to the care of pediatric oncology patients.⁸ Pediatric oncology departments such as the Memorial Sloan Kettering Cancer Center (MSKCC) Department of Pediatrics have adopted institutional practices in an effort to reduce bone-marrow procedure-related pain and anxiety. The standard of care at MSKCC for pediatric patients undergoing BMA and BMB is to receive propofol. While propofol has amnestic and anesthetic properties, it lacks any analgesic properties.⁹

3.2 Needs assessment

In order to better understand bone marrow procedural pain for pediatric patients at MSKCC, we conducted a needs assessment of 25 pediatric patients and 1 adult patient, asking about their experience with BMA and BMB, done with the standard of care administration. We found that 8/26 = 30.7% of patients required opioid analgesia within 24 hours of the procedure - 7/8 post-procedurally and one patient with systemic opioid given with anesthesia. We also discovered that many children had persistent pain and reduced activity level the day following the procedure - 12/26 = 46% and 8/26 = 31%, respectively. Based on this data, we identified a need to improve the experience of pediatric neuroblastoma patients with bone marrow procedures. Although there are no standard clinical guidelines, the AAP recommends an individualized and age-based approach and encourages the use of both non-pharmacologic and pharmacologic interventions that includes both anesthesia and analgesia.⁸ We also conducted an informal survey of seven other major pediatric oncology centers and found that each of these centers uses analgesia, either systemic or local, in addition to general anesthesia for bone marrow biopsy procedures.

3.3 Rationale

The purpose of this study is to investigate whether subcutaneous and periosteal infiltration of a local anesthetic agent, ropivacaine, will reduce the percentage of patients requiring post-procedural opioid analgesia and improve quality of life in the day following the procedure. A similar study recently demonstrated that topical analgesia for lumbar punctures reduced the amount of propofol used in pediatric oncology patients.⁹ However, no study has been done to investigate the efficacy of local analgesia in combination with propofol for bone marrow procedures. For this reason, a trial evaluating the effect of the addition of local analgesia is both justified and necessary. Local analgesia acts to limit the initiation of nociceptive pathways prior to the traumatic insult, in this case, subcutaneous and periosteal infiltration by a bone marrow aspiration or biopsy needle. Ropivacaine is an example of a local anesthetic agent that blocks both the initiation and conduction of nerve impulses by decreasing the neuronal membrane's permeability to sodium ions.¹⁰ It is an amino-amide local anesthetic that is a pure S-(-)-enantiomer with lower lipid solubility than racemic mixtures; these features allow ropivacaine to have a higher safety profile with less cardiovascular and central nervous system toxicity than racemic lidocaine and bupivacaine.¹⁰ Its onset of action is listed as "fast" with infiltration. i.e. within 3 to 15 minutes.¹¹ Its duration of action is 3 to 15 hours.¹¹ Therefore, due to its effect on nociceptive pathways, rapid onset and moderate duration of action while maintaining a low toxicity profile, ropivacaine is a reasonable option for local analgesia for bone marrow procedures. This is the first time ropivacaine will be directly injected into the bone marrow site at MSKCC Pediatrics.

Primary and secondary outcome measures were carefully selected after reviewing pediatric pain literature. Within pain clinical trials, analgesic efficacy can be measured by the ability to reduce or eliminate the need for rescue analgesia. "Rescue analgesia-sparing" has been identified as practical and feasible surrogate primary endpoint^{12,13}. A systematic review of

33 pediatric trials that used opioid as the study drug showed that percentage requiring rescue medication was a useful outcome measure in small procedures when the time and amount of rescue medication needed was low relative to surgical procedures.¹³ This will be the primary outcome in the current study. Time to first rescue opioid and total opioid dose were alternate outcomes that are commonly studied;¹³ in this protocol, they are selected as secondary outcomes. Relative differences in pain scores, either over time or with an intervention, are frequently used as an outcome measure in pain clinical trials and will be a secondary outcome in this study.^{1, 2, 15} We selected the Wong-Baker FACES® Pain Rating Scale (WBFPRS) (Appendix 1) for this study because it is a validated scale intended for use for our patient population.^{14, 15} Advantages of this scale include its reliability over time, ease of administration, and children have been shown to prefer this scale over others.¹⁵ It is routinely used clinically at MSKCC Department of Pediatrics. An extensive review of various pediatric pain scales concluded that many of the pain scales in use are equivalent, and encouraged the use of a scale familiar to the institution for clinical purposes.¹⁶

This study will use a pain management algorithm for consistency in post-procedural pain management (Appendix 2.1 and 2.2). This algorithm relies on the WHO Analgesic Ladder for escalation of therapy. We referred to the previously mentioned needs assessment as well as commonly used categories for pain severity to determine the interventions starting from heat packs, moving to the non-opioid analgesic: acetaminophen and escalating to a low dose strong opioid for moderate pain as defined as pain greater than but not equal to a 4 on the WBFPRS. The decision to use a low dose strong opioid instead of a weak opioid as suggested by the WHO Analgesic Ladder is based both on institutional practice and recent multi-center study in patients with cancer and moderate pain demonstrating better pain relief with a low dose strong opioid instead of weak opioid.¹⁷

Groups such as the Pediatric Initiative on Methods, Measurement, and Pain Assessment in Clinical Trials (PedIMMPACT) have recommended multidimensional outcome domains and measures for pediatric pain clinical trials.^{15, 18} The PedIMMPACT consensus guidelines for investigators conducting clinical trials addressing acute pain include 6 domains including pain intensity, physical recovery and emotional response.¹⁸ We aim to incorporate these additional domains into this study by utilizing a quality of life metric adapted from a validated pain interference inventory. We will use an abbreviated version of the National Institutes of Health (NIH) Patient Reported Outcomes Measurement Information System (PROMIS®) Parent Proxy measure for pain interference.^{19, 20} This full item bank has been validated for use by the parents of 8-17 year olds and has been extended for use in 5-7 year olds.^{19, 20} We will extrapolate its use for our patient population and have selected 4 of the 13 items from the item bank to assess how procedural pain affects physical recovery in the context of activity and sleep as well as social and emotional functioning (Appendix 3).

This study is clinically relevant in the care of pediatric neuroblastoma patients who undergo repeated painful procedures in an effort to optimize pain alleviation and reduce the potential for distress related to procedures. We specifically selected pediatric neuroblastoma

patients since they undergo repeated bone marrow procedures during the course of their care and these procedures often involves four sites. Therefore, it would benefit these young patients to identify pain associated with recurrent procedures and optimize its management. We have selected a single patient population to allow for better standardization in our assessment and outcome measures. As a result of this study, we hope to improve standard institutional practice for any pediatric patient undergoing a bone marrow procedure.

4.1 OVERVIEW OF STUDY DESIGN/INTERVENTION

4.2 Design

This study will be a prospective double-arm randomized controlled single-blinded crossover design. The two interventions are:

- Intervention A: MSKCC standard of care
- Intervention B: MSKCC standard of care *plus* local analgesia with ropivacaine.

Pediatric neuroblastoma patients will be enrolled based on eligibility criteria and randomized to one of two arms representing a specific sequence of each intervention.

- Arm 1 (AB): standard of care only during the first procedure, then standard of care plus ropivacaine during the second procedure.
- Arm 2 (BA): Standard of care plus ropivacaine during the first procedure, then standard of care only during the second procedure.

Each patient will serve as his or her own control. The patients and parents will be blinded to the study arm. The procedural attending physicians and pharmacy will have to coordinate and administer the treatment agent (ropivacaine), and they will not be blinded to the study arm. The registered nurse (RN) in the procedure room will similarly not be blinded to the study. The Pediatric Day Hospital (PDH) Procedure Recovery Room (PRR) RNs will be blinded as they will also be responsible for data collection as described below. The study investigators who will be responsible for post-procedural data collection will similarly be blinded to the study combination.

4.3 Intervention

Intervention A: The standard of care agent will be administered intravenously by an anesthesiologist as per current institutional practice. An empty decoy syringe will be provided by the pharmacy and taken to the procedure room by appropriate staff as sometimes parents accompany their children into the procedure room prior to anesthesia administration. The empty syringe will be clearly marked and discarded.

Intervention B: The standard of care agent will be administered intravenously by an anesthesiologist as per current institutional practice. Once the anesthetic effect is achieved as determined by the anesthesiologist, the proceduralist physician will inject subcutaneous and periosteal ropivacaine prior to bone marrow aspiration and biopsy at each site (bilateral anterior and posterior iliac crests). Ropivacaine will be provided by the MSKCC PDH Pharmacy and will

be administered at standard dosing of 2mg/kg of a 0.5% solution (5mg/ml) and delivered to the procedure room by appropriate staff.

The following process occurs after every procedure. Patients will complete the procedure and recover in the PRR for an approximate time of 30 to 90 minutes. In the PRR, trained RNs who are blinded to the study combination will assess patient pain based on a validated self-report pain scale and administer pain medication when necessary based on a standard pain management algorithm (Appendix 2.2). After recovery in the PRR, patients will be discharge home. Parents/parents will assess their child's pain on a validated self-report pain scale and administer pain medication when necessary based on a standard pain management algorithm (Appendix 2.2).

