5.0 THERAPEUTIC/DIAGNOSTIC AGENTS

5.1 Study agent: ROPIVACAINE^{11, 25-28}

5.1.1 Source and Pharmacology: A local anesthetic. Mechanism of action is by blockade of both the initiation and conduction of nerve impulses by decreasing the neuronal membrane's permeability to sodium ions, which results in inhibition of depolarization with resultant blockade of conduction. The half-life is 5 to 7 hours when used as an epidural infusion and has a terminal half-life of 111 ± 62 minutes. It is metabolized by the liver and excreted through the urine.

5.1.2 Formulation and Stability: Supplied in single-dose containers in 2 mg/ml (0.2%), 5 mg/ml (0.5%), 7.5 mg/ml (0.75%) and 10 mg/ml (1%). Store at 20°C to 25°C.

In this study, the PDH pharmacy will prepare four (4) syringes from a single vial of the 5mg/ml (0.5%) ropivacaine at a dose of 2mg/kg/patient divided evenly into 0.5mg/kg/syringe with a maximum dose of a single 20 ml vial = 100 mg.

5.1.3 Guidelines for Administration: Doses are administered via local infiltration.

5.1.4 Supplier: Commercially available. See package insert for further information.

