9.0 TREATMENT/INTERVENTION PLAN

Each enrolled patient will serve as his/her own control. On two bone marrow procedures, patients will receive either **intervention A** or **B**.

Each procedure will occur at approximately a two to four month interval. The timing of bone marrow procedures will be determined by the patient's clinical course.

In Intervention A, standard of care dosing and administration will be at the discretion of the anesthesiologist according to standard of care in the Department of Anesthesia at Memorial Sloan Kettering Cancer Center. In Intervention B, 2mg/kg of 0.5% ropivacaine will be drawn into

pre-filled syringes with a maximum dose of 20ml = 100mg. The physician performing bone marrow procedures will administer ropivacaine.

Ropivacaine will be injected into the subcutaneous tissue in an area approximately 1 cm in diameter. Subsequently, the ropivacaine will be administered to the periosteum in an area approximately 2-3 cm in diameter. Four pre-filled syringes will be provided and proceduralist physicians will be advised to administer one full syringe volume for each site (0.5mg/kg) with equal distribution between the subcutaneous and periosteal injection per site. Currently, propofol alone is the standard of care in the Department of Pediatrics at Memorial Sloan Kettering Cancer Center. While ropivacaine is a well described local anesthetic agent, the addition of ropivacaine to propofol to minimize post procedure pain is an experimental intervention.

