10.0 EVALUATION DURING TREATMENT/INTERVENTION

Pain will be assessed in the post-anesthesia care unit (PRR). Directly upon emergence from anesthesia after the procedure and every 15 minutes subsequently, PRR nurses will use the Wong-Baker FACES® Pain Rating Scale (Appendix 1). Nurses will record patient-reported pain scores and administered analgesia in the Electronic Medical Record (EMR). Analgesia doses will be recorded at the time of administration. The PRR nurses will follow a standardized post-procedural algorithm (Appendix 2.1). Patients will recover in the PRR for approximately 30 to 90 minutes prior to discharge from MSKCC. In some instances, patients will be discharged from the PRR to the Neuroblastoma Clinic in the Pediatric Day Hospital (PDH). We anticipate that all patients will be discharged from MSKCC before 6 hours from the end of their procedure. In the unexpected case that a patient is admitted to the hospital for any reason during the study period (28 hours post-procedure), study investigators will provide the inpatient RN with the post-procedural opioid management algorithm (Appendix 2.1). Only if the admission is due to a study related life-threatening grade 4 toxicity, will the admitted patient be removed from the study as described in Section 13.0.

Families will be provided a 2 part, 12 item written questionnaire with 4 items and 8 items in each part, respectively (Appendix 3). They will be asked to complete Part 1 at 6 hours (+/- 1 hour) and Part 2 at 24 hours (+/- 4 hours) following the procedure. This questionnaire will have items regarding pain intensity and management to be answered at both time points. Families will be asked to follow a post-procedure pain management plan (Appendix 2.2). Post-procedural quality of life (QOL) will be assessed using a four-item questionnaire (Appendix 3) adapted from the NIH PROMIS® Parent Proxy Item Bank for Pain Interference and approved for use by the MSKCC Behavioral Research Methods Core Facility. These four questions will include the domains of physical recovery, emotional and social functioning. QOL will be assessed about 24 hours (+/- 4 hours) following the procedure. Principal Investigators, Co-Investigators, Investigators or appropriate clinic staff will call families 24-72 hours following procedure to obtain answers to the questionnaire.

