12.0 CRITERIA FOR THERAPEUTIC RESPONSE/OUTCOME ASSESSMENT

12.1 To assess primary objective, we will determine and compare for each study intervention the percentage of patients who required opioid analgesia between the time of bone marrow procedure and 24 hours (+/- 4 hours) after the procedure.

12.2 For the secondary objectives:

- a) We will determine and compare for each study intervention the percentage of patients who used any non-opioid analgesia within 24 hours (+/- 4 hours) after bone marrow procedure.
- b) We will calculate and compare for each study intervention the total dose of opioid consumption within 24 hours (+/- 4 hours) of the bone marrow procedure using mg/kg/day morphine equivalent.

Drug	IV conversion factor	PO conversion factor
Morphine	10mg	30mg
Fentanyl	0.250mg (250mcg)	—
Hydromorphone	2mg	8mg
Oxycodone	—	20mg
Oxymorphone	1mg	10mg
Codeine	75mg	130mg
Methadone	1mg	2mg
Hydrocodone	—	30mg

c) We will also determine the time to the first opioid administration. The starting point for this time will be the time of transfer to the PRR which will be documented by the PRR RN. This time will be recorded on the parent worksheet by the PRR RN.

d) We will assess standardized pain scores at 3 time points: (1) the maximum recorded pain score in the PRR, (2) at 6 hours (+/- 1 hour) and (3) 24 hours (+/- 4 hours) after the bone marrow procedure. Pain scores 2 and 3 will be recorded by the parent after discharge from MSKCC. We will use the following validated pain scales: Wong-Baker FACES® Pain Rating Scale for patients between 3-18 years of age for patient-reported pain when asked by post-anesthesia recovery room nurses upon emergence from anesthesia and by inpatient nurses or family members in the outpatient setting upon discharge from the post-anesthesia recovery unit. We will compare pain scores between study interventions.

e) The QOL metric is a brief instrument that will assess post-procedural quality of life within 24 hours (+/- 4 hours) of the bone marrow procedure. This instrument assesses the following domains: sleep, physical functioning, emotional functioning and social functioning. This brief measurement tool will be adapted from a validated metric for pain interference in pediatric patients: NIH PROMIS® Parent Proxy Item Bank v1.0 – Pain Interference, which is a 13-item questionnaire. However, given that our study has rapid, frequent assessments, we will use an

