abbreviated version for feasibility purposes and to minimize participant burden. Parents will be asked to assess QOL at 24 hours (+/- 4 hours) following the procedure by completing the questionnaire at that time. Principal Investigators or Research Staff will call families 24-72 hours following procedure to obtain answers to survey. This phone call will be for the purposes of data collection only and not for survey administration.

f) Patients will be under medical observation during the expected time when most adverse effects from ropivacaine will be experienced. Families will be advised to call the hospital for any symptoms beyond this time period.

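### The Intervention A decoy is one empty, marked syringe against four filled ones in Intervention B, so a parent who sees them could infer the arm.

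*Combined protocol and SAP*

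**What the plan says.** Section 4.2 states the blind without qualification: "The patients and parents will be blinded to the study arm". The procedural attendings, pharmacy and procedure-room nurse are unblinded; the recovery-room nurses are blinded.

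Section 4.3 describes the masking measure for Intervention A: "An empty decoy syringe will be provided by the pharmacy and taken to the procedure room by appropriate staff as sometimes parents accompany" their children before anesthesia is given. It adds: "The empty syringe will be clearly marked and discarded".

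For Intervention B, section 5.1.2 says that "the PDH pharmacy will prepare four (4) syringes from a single vial", and section 9.0 says "Four pre-filled syringes will be provided", one for each site.

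On who produces the data, section 10.0 says "We anticipate that all patients will be discharged from MSKCC before 6 hours from the end of their procedure". Section 4.3 has parents assess pain and give medication at home under the algorithm. Section 12.2(d) says of the 6-hour and 24-hour scores: "Pain scores 2 and 3 will be recorded by the parent after discharge from MSKCC". Section 12.2(e) says "Parents will be asked to assess QOL at 24 hours", with a window of 4 hours either side.

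**The concern.** The decoy exists for one situation, a parent in the procedure room before anesthesia. In that situation it does not resemble what it stands in for: one syringe against four, empty against filled. The crossover adds to the problem. Each family has one procedure of each kind, so a parent present at both can compare them, and identifying either one reveals the other.

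The parent is not a bystander to the outcome. The primary endpoint is any opioid use from the procedure to 24 hours (+/- 4 hours), and most of that time is spent at home. A parent who believes the child received only standard care may ask about pain differently or medicate sooner. That would push the home part of the primary endpoint, the later pain scores and the proxy quality-of-life items towards ropivacaine. The quality-of-life items are the most exposed, because the parent is the rater.

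**Working it through.** **1. The two set-ups side by side**

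| Feature | Intervention A | Intervention B |
|---|---|---|
| Number | one (4.3, singular in both sentences) | four (5.1.2 and 9.0) |
| Content | empty | filled, 0.5 mg/kg each at 5 mg/ml |
| Marking | clearly marked (4.3) | not stated |
| Covering or packaging | not stated | not stated |

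Each B syringe holds 0.5 mg/kg ÷ 5 mg/ml = 0.1 ml/kg. For an illustrative child of 30 kg that is 3 ml, against 0 ml in the decoy. The firm differences are number and content. The marking may or may not separate the arms, because the labelling of the B syringes is not given.

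**2. Share of the primary window at home**

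Discharge is expected before 6 hours (10.0). Time at home is then at least 24 − 6 = 18 hours. At the ends of the +/- 4 hour window it is 20 − 6 = 14 and 28 − 6 = 22 hours. The share of rescue opioids given at home is not stated.

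**3. Reproducing the plan's power**

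Inputs from section 14.0: 45 pairs, rates 30% (A) and 10% (B), correlation 0.4, alpha 0.05, exact conditional McNemar test. Two-sided testing is assumed, since the plan does not say.

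- Both procedures with opioid: p11 = pA·pB + r·√[pA(1−pA)·pB(1−pB)] = 0.03 + 0.4 × √(0.21 × 0.09) = 0.0850.
- Opioid under A only: 0.30 − 0.0850 = 0.2150. Under B only: 0.10 − 0.0850 = 0.0150.
- Summing the exact binomial rejection probability over the number of discordant pairs gives 80.9%, matching the stated 80%.

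**4. Illustration of bias with no true effect**

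The same calculation, with both true rates at 30% and an assumed artificial gap spread evenly around 30%. The result is the probability of rejecting in favour of ropivacaine.

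| Average gap (points) | Rates A / B | False positive favouring B |
|---|---|---|
| 0 | 30 / 30 | 1.2% |
| 1 | 30.5 / 29.5 | 1.7% |
| 2 | 31 / 29 | 2.3% |
| 4 | 32 / 28 | 4.1% |
| 5 | 32.5 / 27.5 | 5.4% |
| 10 | 35 / 25 | 17.1% |

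The zero-gap figure is below the nominal 2.5% per side because the exact test is conservative.

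The gap is an average over all families: share unblinded × gap among those families. Thus 0.2 × 10 = 2 points (2.3%), 0.2 × 20 = 4 points (4.1%) and 0.5 × 10 = 5 points (5.4%). Both the shares and the gaps are assumptions; no figure in the documents supports a particular value.

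**The case against.** The sponsor saw this exposure and put a measure in place. Parents are in the room only sometimes and only before anesthesia. The singular wording in section 4.3 may be loose drafting for a set. Handling details such as trays and covers can reasonably be left to pharmacy procedures, so silence does not show that the syringes are in view. What families are told to expect is unknown here, because the consent pages are not in the documents reviewed; a parent at a first visit may learn little from a syringe count.

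The primary endpoint also has safeguards. Pain is self-reported by the child, section 3.3 ties opioid use to a score above 4, section 13.0 removes patients given analgesia outside the algorithm, and blinded nurses give the first medication. The quality-of-life analysis is declared exploratory. Finally, the percentages above come from exact McNemar, whereas the planned primary analysis is a logit GEE, and they ignore the futility look.

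Much of this stands as a limit on size. Exposure is partial, the safeguards reduce bias, and the percentages are illustrative. The plan says the GEE reduces to McNemar's test with complete data, but the GEE need not share the conservatism of the exact test, so the baseline could differ. None of this closes the gap. The decoy is described in the singular twice and the B syringes are counted as four twice. If a matched or covered set was intended, no section says so. The safeguards still leave the parent to elicit the score, give the medication and rate quality of life.

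**Conclusion.** The concern holds. The stated masking measure for Intervention A differs from Intervention B in number and fill, in the one setting it was written for, and no other section makes up the difference. This is a risk to the parental blind, not proof that it fails.

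Its size cannot be worked out from the documents, because parental presence, visibility of the syringes and the share of opioids given at home are not stated. If few parents see the syringes, the primary test is little affected. If half of families were unblinded with a 10-point gap each, the false-positive rate favouring ropivacaine would rise from 1.2% to 5.4%, given 45 pairs, correlation 0.4, a 30% rate and a two-sided exact McNemar test. The proxy quality-of-life items are the most exposed. The point should be corrected. Confidence is medium, because the extent of exposure is unknown.

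**What to change.** Amend section 4.3 in one of two ways.

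1. **Matched packaging.** Both interventions arrive in the same sealed opaque outer package holding four syringes, opened only after any parent has left. The decoys stay clearly marked inside for the unblinded proceduralist and procedure-room nurse, and are discarded unused as now. Cost: three more empty syringes and one opaque package per control procedure. The marking is hidden until opening, so unblinded staff must check it then.
2. **Timing.** For both interventions, the syringes enter the room or are uncovered only after the parent has left. Cost: no material, only the timing of delivery, and the current marking stays as it is.

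In either case, add a tick-box recording whether a parent was in the room before anesthesia, so that exposure can be described. The section 16.0 data list has no such item. The tick-box records opportunity rather than unblinding; asking parents to guess the intervention after each procedure would measure the blind more directly. None of this changes the dose, the sample size or the analysis, and nothing is injected under Intervention A.
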